10.2 Patient data protection

The ICF will incorporate (or, in some cases, be accompanied by a separate document incorporating) wording that complies with relevant data protection and privacy legislation.

If mandatory genetic testing is required on any of the STRONG modules, the following applies. AstraZeneca will not provide individual genotype results to patients, any insurance company, any employer, their family members, general physician, unless required to do so by law.

Precautions will be taken to preserve confidentiality and prevent genetic data being linked to the identity of the patient. In exceptional circumstances, however, certain individuals might see both the genetic data and the personal identifiers of a patient. For example, in the case of a medical emergency, an AstraZeneca Physician or an Investigator might know a patient's identity and also have access to his or her genetic data. Also, regulatory authorities may require access to the relevant files, though the patient's medical information and the genetic files would remain physically separate.

Each patient will be assigned a unique identifier by the Sponsor. Any patient records or data sets transferred to the Sponsor will contain only the identifier; patient names or any information which would make the patient identifiable will not be transferred.

The patient must be informed that his/her personal study-related data will be used by the Sponsor in accordance with local data protection law. The level of disclosure must also be explained to the patient.

The patient must be informed that his/her medical records may be examined by Clinical Quality Assurance auditors or other authorized personnel appointed by the Sponsor, by appropriate IRB/IEC members, and by inspectors from regulatory authorities.

10.3 Ethics and regulatory review

An EC (ie, IRB and Independent Ethics Committee [IEC]) should approve the final study protocol, including the final version of the ICF and any other written information and/or materials to be provided to the patients. The Investigator will ensure the distribution of these documents to the applicable EC, and to the study site staff.

The opinion of the EC should be given in writing. The Investigator should submit the written approval to AstraZeneca before enrollment of any patient into the study.

The EC should approve all advertising used to recruit patients for the study.

AstraZeneca should approve any modifications to the ICF that are needed to meet local requirements.

If required by local regulations, the protocol should be re-approved by the EC annually.

Before enrollment of any patient into the study, the final study protocol, including the final version of the ICF, is approved by the national regulatory authority or a notification to the national regulatory authority is done, according to local regulations.

AstraZeneca will handle the distribution of any of these documents to the national regulatory authorities.

AstraZeneca will provide regulatory authorities, ECs and Principal Investigators with safety updates/reports according to local requirements.

Each Principal Investigator is responsible for providing the ECs with reports of any serious and unexpected adverse drug reactions from any other study conducted with tremelimumab. AstraZeneca will provide this information to the Principal Investigator so that he/she can meet these reporting requirements.

In Japan:

An IRB should approve the final study protocol, including the final version of the ICF and any other written information and/or materials to be provided to the patients. The head of the study site will ensure the distribution of these documents to the applicable IRB, and the Principal Investigator to the Investigator and study site staff.

The opinion of the IRB should be given in writing. The head of the study site should submit a notification of direction/determination as well as the IRB written approval to AstraZeneca and the Principal Investigator before enrollment of any patient into the study.

The IRB should approve all advertising used to recruit patients for the study.

AstraZeneca should approve any modifications to the ICF that are needed to meet local requirements.

The head of the study site should seek the opinion of the IRB with respect to the appropriateness of continuing the study at the study site at least once a year when the duration of the study exceeds one year. The Principal Investigator should submit progress reports to the IRB via the head of the study site at the time of the protocol re-approval.

Before enrollment of any patient into the study, the final study protocol, including the final version of the ICF, should be approved by the national regulatory authority with notification provided, according to local regulations. AstraZeneca will handle the distribution of any of these documents to the national regulatory authorities.

AstraZeneca will provide Regulatory Authorities, IRB, the head of the study site and the Principal Investigator with safety updates/reports according to local requirements.

The head of the study site should submit a written report to the IRB providing the details of all safety relative information reported by AstraZeneca.

10.4 Informed consent

The Principal Investigator(s) at each center will:

- Ensure each patient is given full and adequate oral and written information about the nature, purpose, possible risk and benefit of the study.
- Ensure each patient is notified that he/she is free to discontinue from the study at any time.
- Ensure that each patient is given the opportunity to ask questions and allowed time to consider the information provided.
- Ensure each patient provides signed and dated informed consent before conducting any procedure specifically for the study.
- Ensure the original, signed ICF(s) is/are stored in the Investigator's Study File.
- Ensure a copy of the signed ICF is given to the patient.

•

Ensure that any incentives for patients who participate in the study as well as any provisions for patients harmed as a consequence of study participation are described in the ICF that is approved by an EC.

10.5 Changes to the clinical study protocol and informed consent form

Study procedures will not be changed without the mutual agreement of the International coordinating Investigator and AstraZeneca.

If there are any substantial changes to the study protocol, then these changes will be documented in a study protocol amendment and where required in a new version of the study protocol (Revised Clinical Study Protocol).

The amendment is to be approved by the relevant EC and if applicable, also the national regulatory authority approval, before implementation. Local requirements are to be followed for revised protocols.

AstraZeneca will distribute any subsequent amendments and new versions of the protocol to each Principal Investigator(s). For distribution to EC see Section 10.3.

If a protocol amendment requires a change to a center's ICF, AstraZeneca and the center's EC are to approve the revised ICF before the revised form is used.

If local regulations require, any administrative change will be communicated to or approved by each EC.

In Japan:

Study procedures will not be changed without the mutual agreement of the Principal Investigator and AstraZeneca. If it is necessary for the study protocol to be amended, the amendment should be submitted to the head of the study site and be approved by its IRB. If applicable, AstraZeneca should submit a notification to the regulatory authority before it is implemented. If a protocol amendment requires a change to a particular center's ICF, then AstraZeneca and the center's IRB should be notified by the Principal Investigator. Approval of the revised ICF by AstraZeneca and by the IRB is required before the revised form is used. If an administrative change is required, such a change should be notified to or approved by each IRB according to local requirements.

10.6 Audits and inspections

Authorized study representatives of AstraZeneca, a regulatory authority, or an EC may perform audits or inspections at the center, including source data verification. The purpose of an audit or inspection is to systematically and independently examine all study-related activities and documents, to determine whether these activities were conducted, and data were recorded, analyzed, and accurately reported according to the protocol, GCP, guidelines of the ICH, and any applicable regulatory requirements. The Investigator will contact AstraZeneca immediately if contacted by a regulatory agency about an inspection at the center.

4.2.1 Safety data	
4.2.2 Efficacy data	
4.2.3 Demographic and baseline characteristics data	32
5. INTERIM ANALYSES	32
5.1 Data Monitoring Committee	32
6. CHANGES OF ANALYSIS FROM PROTOCOL (NOT APPLICABLE)	33
7. REFERENCES	33
8. APPENDIX	33
8.1 Appendix 1 imAE charter (v6 27Apr2020).	33

LIST OF ABBREVIATIONS

Abbreviation or special term	Explanation
AE	Adverse event
AESI	Adverse event of special interest
ALP	Alkaline phosphatase
ALT	Alanine transaminase
AST	Aspartate transaminase
BMI	Body mass index
BoR	Best Objective Response
CI	Confidence interval
CR	Complete Response
CRF	Case Report Form
CSP	Clinical Study Protocol
CSR	Clinical Study Report
CTC	Common Terminology Criteria
CTCAE	Common Terminology Criteria for Adverse Event
CV	Coefficient of variation
DAE	Discontinuation of investigational product due to adverse events
DBL	Database lock
DCO	Data cut off
DCR	Disease control rate
DMC	Data monitoring committee
DSUR	Development safety update report
ECG	Electrocardiogram
ECOG	Eastern Cooperative Oncology Group
eCRF	Electronic Case Report Form
HL	Hy's Law
ILD	Interstitial lung disease
imAE	Immune-mediated AE
IPD	Important protocol deviation

Abbreviation or special term	Explanation
IV	Intravenous
LDH	Lactate dehydrogenase
MedDRA	Medical Dictionary for Regulatory Activities
NCI	National Cancer Institute
NIH	National Institute of Health
OAE	Other significant adverse events
ORR	Overall response rate
OS	Overall survival
PD	Progressive disease
PD-L1	Programmed death ligand 1
PR	Partial response
PSUR	Periodic safety update report
PT	Preferred term
Q4w	Every 4 weeks
RECIST1.1	Response Evaluation Criteria In Solid Tumors, Version 1.1
SAE	Serious adverse event
SAP	Statistical analysis plan
SD	Stable disease
SI	International system (of units)
SMS	Signal management system
SOC	System organ class
SS	Safety analysis set
Т3	Tri-iodothyronine
T4	Thyroxine
TEAE	Treatment-emergent adverse event
TSH	Thyroid-stimulating hormone
TTE	Time to event
TTR	Time to resolution
ULN	Upper limit of normal
WHO	World Health Organization

AMENDMENT HISTORY

Date	Brief description of change
25May2017	Initial version 1.0
12Jun2020	Amendment v2.0 includes updates consistent with protocol amendment v5.0 regarding DCO and final analysis; clarifications regarding important protocol deviations; additional subgroup analyses for selected endpoints (OS, ORR, DCR, and AEs); and other minor changes to ensure consistency.
Date of last signature	Added the possibility that descriptive data from the study may be utilized as supporting evidence for health authority considerations; update of imAE characterization charter version (Appendix 1).

1. STUDY DETAILS

1.1 Study objectives

1.1.1 Primary Objective

The primary objective is to assess the incidence, severity, nature, seriousness, intervention/treatment, outcome, and causality, including immune-relatedness, of adverse events of special interest (AESIs) in patients who are treated with fixed doses of durvalumab and tremelimumab combination therapy or durvalumab monotherapy.

An AESI is one of scientific and medical interest specific to understanding of the Investigational Product. AESIs for durvalumab \pm tremelimumab include but are not limited to events with a potential inflammatory or immune-mediated mechanism and which may require more frequent monitoring and/or interventions such as steroids, immunosuppressants and/or hormone replacement therapy. An immune-mediated adverse event (imAE) is defined as an AESI that is associated with drug exposure and is consistent with an immune-mediated mechanism of action and where there is no clear alternate aetiology.

AESIs observed with durvalumab or tremelimumab include pneumonitis, hepatitis, diarrhea/colitis, intestinal perforation, endocrinopathies (hypo- and hyperthyroidism, adrenal insufficiency, hypophysitis/hypopituitarism and type I diabetes mellitus), nephritis, rash/dermatitis, myocarditis, myositis/polymyositis, pancreatitis, and rare/less frequent imAEs including neuromuscular toxicities such myasthenia gravis and Guillain-Barré syndrome. Other inflammatory responses that are rare/less frequent with a potential immune-mediated etiology include, but are not limited to pericarditis, sarcoidosis, uveitis and other events involving the eye, skin, hematological and rheumatological events, vasculitis, non-infectious meningitis and non-infectious encephalitis. It is possible that events with an inflammatory or immune mediated mechanism could occur in nearly all organs. In addition, infusion-related reactions and hypersensitivity/anaphylactic reactions with a different underlying pharmacological etiology are also considered AESIs.

1.1.2 Secondary Objectives

The secondary objectives are:

- 1. To assess the incidence, severity, nature, seriousness, intervention/treatment, outcome, and causality of treatment-emergent adverse events (AEs) (including serious adverse events [SAEs]).
- 2. To assess the incidence and frequency of durvalumab \pm tremelimumab) interruption and discontinuation due to treatment-emergent AEs (including SAEs).
- 3. To assess overall survival (OS). Patients will be followed for survival until the final data cut-off (DCO).

1.1.3 Exploratory objective

The exploratory objective is to assess overall response rate (ORR) and disease control rate (DCR) based on investigator assessed response to treatment.

1.2 Study design

This is an open-label, multi-center, study to determine the safety of fixed doses of durvalumab 1500 mg and tremelimumab 75mg combination therapy or durvalumab 1500 mg monotherapy in patients with advanced solid malignancies.

The study consists of separate modules. The study design is common to all the modules and is described in the core protocol. The specificity of each module is described in the tumor specific modules. The specificity of each module might include type of tumor, whether the treatment is combination or monotherapy and whether the study population is on second line or first line of treatment.

The core protocol (and each tumor specific module) consists of a screening period, a treatment period, a safety follow-up period (90 days post treatment discontinuation), and a survival follow-up period.

Patients will attend a safety follow up visit 90 days after study treatment discontinuation.

Thereafter, patients will be contacted by phone or electronic communication every 3 months for survival status until the final DCO.

Investigational product, dosage and mode of administration

Durvalumab + tremelimumab combination therapy

- Durvalumab 1,500 mg plus tremelimumab 75mg via intravenous (IV) infusion once every 4 weeks (Q4w), starting on Week 0, for up to a maximum of 4 doses (or cycles) followed by:
- Durvalumab monotherapy 1,500 mg via IV infusion Q4w, starting 4 weeks after the last infusion of the combination or discontinuation of tremelimumab.

OR

Durvalumab monotherapy

• Durvalumab 1,500 mg via IV infusion Q4w, starting on Week 0.

Each tumor specific module will specify combination therapy or monotherapy, and will provide details of infusion duration.

Duration of treatment

Patients may continue receiving therapy as long as they are continuing to demonstrate clinical benefit, as judged by the Investigator, and in the absence of initiation of alternative cancer treatment, unacceptable toxicity, withdrawal of consent, or other reason for treatment discontinuation.

Unless specific treatment discontinuation criteria are met, patients will continue therapy until disease progression.

Progression during treatment

Patients may continue receiving therapy in the setting of unconfirmed progressive disease (PD), at the Investigator's discretion, until PD is confirmed*. Patients with PD by RECIST 1.1 (unconfirmed and confirmed) who, in the Investigator's opinion, continue to receive benefit from their assigned treatment and who meet the criteria for treatment in the setting of PD may continue to receive treatment for as long as they are gaining clinical benefit.

However, patients will not be permitted to continue immunotherapy if progression occurs after confirmed response (CR or PR as defined by RECIST 1.1) to immunotherapy treatment in target lesions (regardless of the appearance of new lesions) i.e., the response and progression events both occurred in the target lesions while receiving immunotherapy during the same treatment period.

Patients in Modules with combination durvalumab + tremelimumab may restart treatment with the combination if they complete the 4 dosing cycles with durvalumab + tremelimumab (with clinical benefit per Investigator judgement) but subsequently have PD during treatment with durvalumab alone and provided they meet eligibility criteria for re-treatment.

[figure not shown]
*Where treatment is discontinued due to progressive disease, it is recommended that a confirmatory scan be performed prior to discontinuation to verify progression. According to Response Evaluation Criteria in Solid Tumors version 1.1 (RECIST 1.1) modified for confirmation of progression, a confirmatory scan is required following an overall time point assessment of PD, no earlier than 4 weeks after the previous assessment of PD.

Follow up of patients post discontinuation of study drug

Patients who have discontinued treatment due to toxicity or symptomatic deterioration, clinical progression, or who have commenced subsequent anticancer therapy, will be followed up until confirmed disease progression and for survival.

Follow up for safety and survival

Patients will attend a safety follow-up visit 90 days after study treatment discontinuation. Thereafter, patients will be contacted by phone or email every 3 months for survival status until the final DCO

Tumor specific modules detail which treatment regimen, combination therapy or monotherapy, will be used.

Patients will continue to receive study treatment as long as they are receiving clinical benefit in the opinion of the Investigator unless any of the criteria for treatment discontinuation are met first.

Survival follow-up will continue until the final DCO.

Data Monitoring Committee (DMC)

Interim safety monitoring will be conducted by a DMC.

1.3 Number of subjects

The primary aim of the study is to further characterise the safety profile of fixed doses of durvalumab and tremelimumab combination therapy or durvalumab monotherapy in patients with advanced solid malignancies. The precise sample size and number of AESI that will be included in this single arm study is not known a priori.

However, the following sample sizes have been planned for individual modules:

Module A - Post-Chemotherapy Urothelial and NonUrothelial Carcinoma of the Urinary Tract

A sample size of between 600-1200 patients is planned for module A – durvalumab monotherapy in patients with post-chemotherapy urothelial and non-urothelial carcinoma of the urinary tract. A sample size of up to 1200 patients would have over 75% probability (based on exact binomial probability) of observing at least ten events for an AESI with a true incidence of 1%.

Illustrations of the precision around categorical endpoints (e.g. proportion of patients with a specific AE, proportion of patients with a specific intervention for an AE or outcome for an AE) of varying incidence that could be calculated in the total population from this study are given in Table 1. The precision is based on an exact binomial CI and is illustrated using a range of sample sizes.

Table 1 95% confidence interval per sample size and event incidence

Sample size	Incidence							
(number of patients)	0.1%	1%	2%	5%	10%	15%	20%	50%
600	0.00-0.6	0.4-2.2	1.0-3.5	3.4-7.1	7.7-12.7	12.2-18.1	16.9-23.4	45.9-54.1
800	0.000.5	0.4-2.0	1.1-3.2	3.6-6.8	8.0-12.3	12.6-17.7	17.3-23.0	46.5-53.5
1000	0.00-0.6	0.5-1.8	1.2-3.1	3.7-6.5	8.2-12.0	12.8-17.4	17.6-22.6	46.8-53.2
1200	0.02-0.05	0.5-1.7	1.3-3.0	3.8-6.4	8.4-11.8	13.0-17.2	17.8-22.4	47.1-52.9

This sample size may also allow the investigation of safety and efficacy outcomes within subgroups of patients.

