4. ANALYSIS METHODS

4.1 General principles

No hypothesis testing is planned for this single arm study. Each module will be summarised separately.

The general principles as mentioned below will be followed throughout the study:

- Descriptive statistics will be used for all variables, as appropriate, and will be presented separately for each module. Descriptive safety and efficacy data from the STRONG study may be utilized as supporting evidence for health authority considerations.
- Continuous variables will be summarized by the number of observations, mean, standard
 deviation, median, minimum, and maximum. For log transformed data it is more
 appropriate to present geometric mean, coefficient of variation (CV), median, minimum
 and maximum. Categorical variables will be summarized by frequency counts and
 percentages for each category.
- Unless otherwise stated, percentages will be calculated out of the population total.
- Exact CIs for proportions will be calculated using the Clopper-Pearson method.
- For percentiles of survival times based on the Kaplan-Meier method (eg, median survival), CIs will be calculated using the default method available in the SAS LIFETEST procedure (ie, the Klein and Moeschberger extension of the Brookmeyer-Crowley method).
- For point-estimates of survival based on the Kaplan-Meier method (eg, for OS at 12 months), CIs will be calculated using the default method available in the SAS LIFETEST procedure (ie, using Greenwood's estimate of standard error and a log-log transformation).
- For continuous data the mean and median will be rounded to 1 additional decimal place compared to the original data. The standard deviation will be rounded to 2 additional decimal places compared to the original data. Minimum and maximum will be displayed with the same accuracy as the original data.
- For categorical data, percentages will be rounded to 1 decimal place.
- SAS® version 9.3 or higher will be used for all analyses.

Baseline will be the last assessment of the variable under consideration prior to the intake of the first dose of study treatment.

All data collected will be listed.

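### SAP 1.3: the 75% chance of ten events holds only from 1190 of the planned 600 to 1200 patients, and one Table 1 interval is impossible

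*SAP*

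**What the plan says.** SAP Section 1.3 gives a range for the module: "A sample size of between 600-1200 patients is planned for module A". It also concedes that the final number is open: "The precise sample size and number of AESI that will be included in this single arm study is not known a priori". The probability statement follows: "A sample size of up to 1200 patients would have over 75% probability (based on exact binomial probability) of observing at least ten events", completed by the words "for an AESI with a true incidence of 1"%.

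Table 1, titled "95% confidence interval per sample size and event incidence", then shows intervals for 600, 800, 1000 and 1200 patients. Its method is stated: "The precision is based on an exact binomial CI and is illustrated using a range of sample sizes". Section 4.1 names the exact method used in the SAP: "Exact CIs for proportions will be calculated using the Clopper-Pearson method". In the 0.1% column the upper limits printed for 600, 800 and 1000 patients are 0.6, 0.5 and 0.6. The cell for 1200 patients reads 0.02-0.05.

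Section 4.1 also says: "No hypothesis testing is planned for this single arm study". The probability statement and Table 1 are therefore the only quantitative support for the sample size in the SAP.

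**The concern.** There are two separate faults.

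1. A probability that rises with the number of patients is attached to a phrase (*up to 1200*) that covers every smaller size, directly after a planned range that starts at half that number. A reader can take the assurance to apply across the range. At the lower end, ten events of a 1% AESI are in fact unlikely.

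2. The interval printed for 1200 patients at 0.1% does not contain 0.1%. It is also far narrower than the interval for 1000 patients in the row above, although the two sample sizes differ by only a fifth.

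The study is meant to inform on uncommon events, and the number ten has a use elsewhere. SAP Section 4.2.1 (long-term tolerability) makes the prevalence and cumulative-incidence plots for an AESI category conditional on at least ten events. The 75% figure does not enter that rule, but a reader may well use it to judge whether those plots will appear.

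**Working it through.** **Part 1: probability of at least ten events**

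Inputs from SAP 1.3: true incidence p = 0.01; threshold ten events; planned n from 600 to 1200. With X ~ Binomial(n, 0.01),

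P(X ≥ 10) = 1 − Σ (x = 0 to 9) C(n, x) · 0.01^x · 0.99^(n − x)

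The plan's own figure comes first: at n = 1200 this gives 0.7589, so *over 75%* is reproduced. Across the planned range:

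| n | Expected events (n × 0.01) | P(X ≥ 10) |
|---|---|---|
| 600 | 6 | 8.3% |
| 800 | 8 | 28.3% |
| 1000 | 10 | 54.3% |
| 1100 | 11 | 66.1% |
| 1189 | 11.89 | 74.92% |
| 1190 | 11.90 | 75.01% |
| 1200 | 12 | 75.9% |

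The statement is true only for n = 1190 to 1200. Between the ends of the range the probability differs by a factor of 75.9 / 8.3 ≈ 9.

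Solving P(X ≥ 10) = 0.75 for p instead gives the incidence at which the 75% assurance is met: 1.98% at n = 600, 1.49% at 800, 1.19% at 1000 and 0.99% at 1200.

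**Part 2: Table 1 at n = 1200 and 0.1%**

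Method: two-sided 95% Clopper-Pearson. With 0 events the lower limit is 0 and the upper limit is 1 − 0.025^(1/n). With 1 event the lower limit is 1 − 0.975^(1/n).

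The other three cells in the column reproduce if n × 0.001 is rounded down to a whole count:

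| n | n × 0.001 | Count used | Exact upper limit | Printed upper limit |
|---|---|---|---|---|
| 600 | 0.6 | 0 | 0.613% | 0.6 |
| 800 | 0.8 | 0 | 0.460% | 0.5 |
| 1000 | 1.0 | 1 | 0.556% | 0.6 |

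For n = 1200 the expected count is 1.2, which the same rule takes as 1:

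| Events in 1200 | Exact 95% CI |
|---|---|
| 0 | 0 to 0.307% |
| 1 | 0.0021% to 0.463% |
| 2 | 0.0202% to 0.601% |
| 3 | 0.052% to 0.729% |

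The upper limit rises with the count, so its minimum is the zero-event value: 1 − 0.025^(1/1200) = 0.307%. A printed upper limit of 0.05% is therefore out of reach. The narrowest exact interval over all counts from 0 to 1200 is 0.307 points wide; the printed one is 0.05 − 0.02 = 0.03 points wide, about a tenth of that. Against the one-event interval, the printed upper limit is too small by a factor of 0.463 / 0.05 ≈ 9, and the printed lower limit too large by 0.02 / 0.0021 ≈ 10.

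In the columns for 1% and above, the cells reproduce apart from 0.1-point rounding differences in four of them, which are not raised here.

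**The case against.** Part 1 is wording, not arithmetic. The value is right at 1200, and *up to* can be read as naming the maximum. The protocol's version history records that Module A's enrolment number was changed from 1200 to up to 1200, so a figure calculated for 1200 may simply have inherited the new phrase (an inference). The SAP does not say that 75% holds throughout the range, and Table 1 already shows precision at the smaller sizes. All of that is fair. It does not help a reader who sees a 600 to 1200 plan followed by one unqualified probability.

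The practical effect is small. SAP amendment 2.0 is dated June 2020, and the protocol expected its final data cut-off in Q2 2020, so a prospective probability guides little by then. The reported AESI intervals will come from observed data. This stands, and it is why the point is minor.

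The cause of the cell error is not established. Moving the decimal in the upper limit alone gives 0.02-0.5, which matches no exact interval either: a lower limit of 0.02 needs two events, whose upper limit is 0.60. A Wilson interval on a fractional 1.2 events gives 0.020 to 0.499, but that is not the method the SAP names. A fault in extracting the text from the PDF also cannot be ruled out, since the 800-patient cell in the same column has lost its hyphen (0.000.5). The 1200-patient cell is well formed, and both limits would have to be misread for the source to be right. If that were the case, part 2 would fall and part 1 would stand.

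**Conclusion.** Both points hold, as minor corrections. The 75% assurance is met at 1190 to 1200 patients and nowhere else in the planned range; at 600 it is 8.3%. This rests only on the SAP's own inputs (1% incidence, ten events, exact binomial). The Table 1 cell at 1200 patients and 0.1% is impossible under the stated exact 95% method for any event count. That conclusion assumes the cell reads in the source document as it does in the text. The replacement value assumes one observed event, consistent with how the rest of the column reproduces; the SAP does not state that rule. No analysis, enrolment decision or stopping rule is affected.

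**What to change.** In SAP Section 1.3, replace the probability sentence with one along these lines:

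> With 1200 patients, the exact binomial probability of seeing ten or more events of an AESI whose true incidence is 1% is 75.9%; with 600, 800 and 1000 patients it is 8.3%, 28.3% and 54.3%.

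The minimum change is to delete *up to*.

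In Table 1, check the cell for 1200 patients and 0.1% against the source PDF and, if it reads as quoted, change 0.02-0.05 to 0.00-0.5 (one event). If the sponsor confirms the rounding rule, a footnote could say that the 0.1% column assumes 0, 0, 1 and 1 observed events at 600, 800, 1000 and 1200 patients.

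The cost is one sentence and one table cell, plus the Module A text if it repeats them. The stated assurance becomes less favourable at the smaller sizes; enrolment and analysis do not change.
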